Table 4: Potentially Clinically Significant Safety Laboratory Values.....	31
Table 5: Potentially Clinically Significant Vital Sign Values	32
Table 6: Abnormal Electrocardiogram Categories	33
Table 7: Potentially Clinically Significant Electrocardiogram Values.....	34
Table 8: PK Parameters	40
Table 9: PROMIS T-Score Conversions for Adult Global Physical and Mental Health.....	45
Table 10: PROMIS T-Score Conversions for Pediatric Global Health	46
Table 11: Flare-up Location Mapping	47

List of Abbreviations

Abbreviation	Definition
AE	adverse event
ATC	anatomic therapeutic class
AP	anterior/posterior
CAJIS	Cumulative Analogue Joint Involvement Scale
C-SSRS	Columbia-Suicide Severity Rating Scale
CSR	Clinical Study Report
CT	computed tomography
CTCAE	Common Terminology Criteria for Adverse Events
ECG	electrocardiogram
eCRF	electronic case report form
FOCBP	Female subjects of childbearing potential
FOP	Fibrodysplasia Ossificans Progressiva
FOP-PFQ	FOP-Physical Function Questionnaire
GEE	generalized estimating equation
HO	heterotopic ossification
LPLV	last patient last visit
MedDRA	Medical Dictionary for Regulatory Activities
NDA	New Drug Application
NHS	Natural History Study
PCS	potentially clinically significant
PROMIS	Patient-Reported Outcomes Measurement Information System
RAR γ	retinoic acid receptor gamma
ROM	range of motion
SAE	serious adverse event
SAP	statistical analysis plan
ULN	upper limit of normal
US	United States
WBCT	whole body computed tomography
wLME	weighted linear mixed effect model

1 Introduction

1.1 Context for Version 1.1

This statistical analysis plan amendment is introduced in preparation for the writing of the final CSR, which will include summaries of data collected after the start of the prolonged palovarotene dosing interruption that started in late 2019/early 2020 described below and up to LPLV in late 2022. This includes data from subjects who restarted palovarotene after the interruption and subjects who did not restart. The final CSR is not intended to include a rerun of tables and content already included in the interim CSRs from 2021 and 2022.

1.2 Context for Version 0.3 (Final)

This Statistical Analysis Plan (SAP) describes the analyses to be performed for Study PVO-1A-202 Part C based on Amendment 4 of the protocol dated 01 September 2017, and all subsequent amendments; along with the France-specific Amendment 2 of the protocol for Study PVO-1A-204 dated 02 November 2017, and all subsequent amendments. Data collected for Study PVO-1A-202 Part C and Study PVO-1A-204 will be combined for the analyses. For the purposes of this SAP, “Study PVO-1A-202 Part C” (or simply “Part C”) represents data from both studies.

The analyses performed for Study PVO-1A-202 Parts A and B are described in separate SAPs. PK analysis is described in this SAP. However, the PK analysis will be performed separately.

The focus of this document is the analyses to be included in an interim CSR for the palovarotene NDA, which will not include summaries of all efficacy endpoints. This SAP may be amended to include additional details of analyses to be performed for the final CSR based on the locked Part C data.

As WBCT and X-Ray bone safety data are collected sequentially from Study PVO-1A-201 through PVO-1A-202C, the combination of bone safety analysis will be provided in the integrated safety analysis. However, listing of bone safety for Part C will be provided in this SAP.

This amendment is introduced after the second interim analysis in Study PVO-1A-301 (“Study 301”) but before the planned third interim analysis (anticipated to be held in mid-May 2020). The futility boundary for Study 301 was crossed at the second interim analysis, signifying that the prespecified Bayesian compound Poisson distribution model with square-root transformation indicated that the trial was unlikely to show sufficient evidence of benefit. The independent data monitoring committee (DMC) informed the sponsor of this outcome on January 15, 2020, and the efficacy assessments were subsequently unblinded to the sponsor.

Based on additional post-hoc analyses presented to the DMC on January 21, 2020, the DMC noted that using the square-root transformation of the data in the primary analysis appears to have moved the statistical conclusion from significant therapeutic benefit to showing futility of the treatment. The DMC also noted that the dilemma created by these highly disparate results precludes a confident conclusion about futility. As such, the DMC recommended that additional analyses be conducted and provided to them for consideration at the next interim analysis.

US FDA instituted a partial clinical hold on dosing of palovarotene due to premature physéal closure (PPC) for subjects <14 years of age on December 4, 2019; as of the finalization of this SAP amendment, dosing

has not yet resumed for these subjects. Dosing on all other subjects in Study 301 and Study 202 Part C not subject to US FDA's partial clinical hold was interrupted following the January 21, 2020 DMC meeting while the protocol amendment allowing the continuation of the study after the futility outcome and incorporating the additional analyses requested by the DMC was reviewed by regulatory agencies, IRBs, and investigational sites. These subjects had palovarotene dosing interrupted on or around January 24, 2020. The sponsor allowed dosing to resume as of March 26, 2020, provided each individual site had obtained Ethics Committee approval to do so and the site was able to fulfil regulatory and operational requirements. Subjects were expected to restart dosing over a span of weeks due to these logistical considerations.

2 Overview

2.1 Study Objectives

2.1.1 Primary Objective

The primary objective is:

- To evaluate the safety and efficacy of different palovarotene dosing regimens in subjects with FOP. Efficacy will be based on the ability of palovarotene to prevent heterotopic ossification (HO) as assessed by low-dose whole body computed tomography (WBCT) scan, excluding head.

2.1.2 Secondary Objectives

- To evaluate the effect of palovarotene on range of motion (ROM) as assessed by the Cumulative Analogue Joint Involvement Scale for FOP (CAJIS).
- To evaluate the effect of palovarotene on physical function using age-appropriate forms of the FOP-Physical Function Questionnaire (PFQ).
- To evaluate the effect of palovarotene on physical and mental health using age-appropriate forms of the Patient Reported Outcomes Measurement Information System (PROMIS) Global Health Scale.
- To evaluate the pharmacokinetics of palovarotene.
- Part D: To implement safety measures recommendations in order to ensure that assessments of safety continue for up to 2 years post last dose of study treatment for skeletally immature subjects.

2.2 Study Design

PVO-1A-202 Part C is a Phase 2, multicenter, open-label extension of Study PVO-1A-202 Part B. This continuation of the open-label extension study will give subjects who participated in Part B the opportunity to be followed for up to an additional 36 months. There will be no new subjects in Part C.

Part D annual post last dose of study treatment assessments for up to 2 years will be obtained in subjects who were skeletally immature at the time of study treatment discontinuation in order to obtain longer-term safety data. No new subjects will be enrolled in Part D. Subjects will follow assessments outlined in Table 4 of the protocol as long as they are not 100% skeletally mature. Part C plus Part D total duration will not exceed 48 months.

Added assessments for spinal health will be carried out on low dose WBCT scans collected in the study.

Non Flare-up Based Treatment

Subjects will follow all procedures and undergo all assessments as specified in the Schedule of Assessments in Table 1 and Table 2 of the protocol. Subjects who cannot receive non-flare-up based treatment will only undergo annual assessments (clinical laboratory tests will not be performed). In the event of a flare-up or traumatic event, these subjects will receive flare-up based treatment and undergo all flare-up based assessments, including clinical laboratory tests and radiographs if they have not reached 100% skeletal maturity.

- **Subjects from Part B Continuing Non-Flare-Up Based Treatment into Part C**

Subjects who began non-flare-up based treatment during Part B will continue this visit schedule into Part C and will receive non-flare-up based treatment for up to an additional 48 months. Therefore, these subjects may undergo non-flare-up based treatment for up to 72 months over the entire study. These subjects will follow all procedures and undergo all assessments as specified in the Schedule of Assessments in Table 1 of the protocol, including low dose WBCT scan (excluding head) at all annual site visits (Months 12, 24, 36, 48, 60 and 72). Non-flare-up Day 1 is the first day that non-flare-up based treatment was initiated during Part B, and total duration of treatment will continue into Part C.

Remote visits (e.g., at home or at a local medical facility; and via telephone contact from clinical site personnel) will occur every 3 months unless the Investigator deems that a site visit is necessary; urine pregnancy tests will be performed each month for female subjects of childbearing potential (FOCBP).

- **Subjects from Part B Starting Non-Flare-Up Based Treatment During Part C**

Subjects who will start non-flare-up based treatment during Part C will receive non-flare-up based treatment for up to 48 months. These subjects will follow all procedures and undergo all assessments as specified in the Schedule of Assessments in Table 2 of the protocol, including low-dose WBCT scan (excluding head) at Screening and at all annual site visits (Part C Screening and Months 12, 24, 36 and 48.). Non-flare-up Day 1 is the first day that non-flare-up based treatment is initiated during Part C for these subjects.

Remote visits (e.g., at home or at a local medical facility; and via telephone contact from clinical site personnel) will occur every 3 months unless the Investigator deems that a site visit is necessary; urine pregnancy tests will be performed each month for female subjects of childbearing potential (FOCBP).

Blood samples for PK assessment of non-flare-up dosing will be collected at the first 3-month safety assessment at pre-dose and 3, 6, 10, and 24 hours post-dose; if samples cannot be or were not obtained at the 3-month safety assessment, or if a subject is on flare-up based treatment, then the PK blood sample for non-flare-up based treatment can be obtained during any subsequent 3-month safety visit.

Flare-up Based Treatment

Subjects receiving flare-up based treatment will follow all procedures and undergo all assessments as specified in the Schedule of Assessments in Table 3 of the protocol. Assessments will occur at Flare-up Cycle Safety Day 1 at 4 weeks, and every 8 weeks thereafter until treatment of the last flare-up or traumatic event in the flare-up cycle is completed. If after 12 weeks all flare-ups have not resolved then additional treatment and assessments will be performed every 4 weeks until all flare-ups have resolved. All assessments will occur remotely unless the Investigator deems it necessary to evaluate subjects at the clinical site. Once all flare-ups or traumatic events in a cycle have resolved and flare-up based treatment has been completed, subjects will resume non-flare-up based treatment with 5 mg palovarotene once daily

(weight-adjusted doses for skeletally immature subjects). Additional knee and hand/wrist radiograph assessments will also be performed every 3 months (± 2 weeks) in skeletally immature subjects who (1) received flare up dosing in the period of time since their last assessment; and (2) had not achieved 100% skeletally maturity on their last assessment.

Off Treatment Part D:

No study drug will be administered in Part D. For skeletally immature subjects in Part D, added Year 1 (Y1) and Year 2 (Y2), post last dose of study treatment assessments that include linear height, knee height, physical exam, vital signs, radiographic assessments of the knee and hand/wrist, low-dose WBCT imaging, adverse events, and concomitant medications. Once subjects reach skeletal maturity their participation in Part D will end. The total duration of participation in Part C and Part D combined is a maximum of 4 years (± 1 month).

Pharmacokinetics

The pharmacokinetics (PK) of palovarotene dosing will be assessed at the first 3-month safety assessment during non-flare-up based treatment; if samples cannot be or were not obtained during the first 3-month safety assessment, or if subjects are on flare-up based treatment, then PK blood samples for non-flare-up treatment can be obtained during any subsequent 3-month safety visit.

Pharmacokinetics (PK) will also be assessed twice during flare-up based treatment: once during the 20-mg regimen at any time between Study Days 4 to 28, and once during the 10-mg regimen at any time between Study Days 32 to 84, for the first treated flare-up only. If this is not possible for the first treated flare-up, PK blood samples can be obtained during any subsequent flare-up dosing cycle. Pharmacokinetic blood samples will be collected at pre-dose and 3, 6, 10, and 24 hours post-dose. Subjects who underwent PK assessment under PVO-1A-202 Protocol Amendment 3 (Part B) will not have PK assessed again; however, these subjects will require a non-flare-up treatment PK assessed at a 3-month safety visit.

2.3 Study Treatment

As of 04 December 2019, all subjects <14 years of age were required to interrupt study drug due to a partial clinical hold placed on the palovarotene clinical development program by the US FDA. Treatment will subsequently not be restarted in children < 14 years of age.

Subjects and/or their parents/caregivers will report potential flare-up symptoms to site personnel; such symptoms include, but are not limited to, pain, swelling, redness, decreased range of motion, stiffness, and warmth. Only one symptom is required to define a flare-up. If these symptoms are consistent with previous flare-ups, include a subject reported onset date, and are confirmed by the Investigator as associated with a flare-up, subjects will receive open-label palovarotene treatment as follows:

- 20 mg for 4 weeks (28 days) once daily. The first dose will be taken upon flare-up confirmation by the Investigator. To be followed by:
- 10 mg for 8 weeks (56 days) once daily, for a total flare-up treatment duration of 12 weeks (84 days); 10 mg treatment may be extended if the flare-up is ongoing and continue until the flare-up resolves. Dosing will be extended in 4-week intervals and be based on clinical signs and symptoms as assessed by the Investigator.

Flare-up based dosing should also be initiated if the Investigator confirms the presence of a substantial high-risk traumatic event likely to lead to a flare-up.

All dosing, regardless of non-flare-up or flare-up based, will be weight-adjusted in subjects under the age of 18 years with less than 90% skeletal maturity on hand/wrist radiography at Screening. (Note: all weight-based dosing will cease when subjects achieve $\geq 90\%$ skeletal maturity based on hand/wrist radiography, but radiographic assessment of the growth plate will continue until these subjects achieve 100% skeletal maturity at both knee and hand/wrist locations.)

Table 1: Weight-Adjusted Palovarotene Doses and Dose De-Escalation Doses

Weight Range Category	20-mg Equivalent	15-mg Equivalent	10-mg Equivalent	7.5-mg Equivalent*	5-mg Equivalent*	2.5-mg Equivalent*
20 to <40 kg	12.5 mg	10 mg	6 mg	4 mg	3 mg	1.5 mg
40 to <60 kg	15 mg	12.5 mg	7.5 mg	5 mg	4 mg	2 mg
≥ 60 kg	20 mg	15 mg	10 mg	7.5 mg	5 mg	2.5 mg

* In the event of dose de-escalation from 20-mg, 10-mg, or 5-mg equivalent, respectively.

If the subject experiences intolerable side effects, the dose may be reduced to the next lower dose; if the subject is already receiving the lowest possible dose as shown in the Table 1, then study drug will be discontinued. Treatment may be extended after the 84-day treatment period (flare-up based dosing) if the flare-up is ongoing and continue until the flare-up resolves. Dosing will be extended in 4-week intervals based on clinical signs and symptoms as assessed by the Investigator, with remote visits performed every 4 weeks while on treatment. In the event the subject requires dose de-escalation due to an intolerable side effect for a previous flare-up, then the dose the subject will receive for a subsequent flare-up will be determined by the Investigator and the Medical Monitor.

Should a subject experience an intercurrent flare-up (defined as a new flare-up or marked worsening of the original flare-up), or if the Investigator confirms the presence of a substantial high-risk traumatic event likely to lead to a flare-up, at any time during flare-up based treatment, the 12-week dosing regimen will restart upon new intercurrent flare-up confirmation by the Investigator (ie, 4 weeks of 20 mg palovarotene followed by 8 weeks of 10 mg palovarotene [or weight-based equivalent]). A Flare-up Cycle will include the first flare-up or traumatic event and any subsequent intercurrent flare-ups or traumatic event during the same dosing period. Flare-Up Cycle Safety Day 1 is defined as the first day that study drug is administered for the first flare-up or traumatic event during that cycle. Safety assessments will be performed on Flare-up Cycle Safety Day 1, at 4 weeks, and every 8 weeks thereafter until treatment of the last flare-up or traumatic event in the Flare-up Cycle is completed. If any flare-up in a cycle has not resolved after 12 weeks, treatment and safety assessments will be extended and 10 mg palovarotene (or the weight-based equivalent) will be administered in 4-week intervals until all the flare-ups resolve and flare-up based treatment has been completed. It is possible that subjects may experience more than one Flare-up Cycle during the study.

2.4 Study Populations

A total of approximately 60 subjects will be enrolled in Part C including up to 40 subjects enrolled from Study PVO-1A-201 and up to 20 new adult subjects enrolled during Part B. All subjects will have participated in Part B and no new subjects will be enrolled in Part C and D.

Flare-up Based Treatment Group:

Flare-up based analyses will be based on flare-up cycles in Part C and will include the treatment group combined PVO 20/10 mg.

Combined PVO 20/10 mg is defined as flare-up cycles that flare-ups were treated with PVO 20/10 mg (or weight-based equivalent) during Part C, regardless of whether non-flare-up PVO 5 mg (or weight-based equivalent) treatment had been administered prior to the flare-up dosing.

Non-Flare-up Based Treatment Group:

Non-flare-up based analyses is based on subjects and will include the treatment group with PVO 5 mg (or weight-based equivalent).

PVO 5 mg group is defined as subjects who received at least one dose of non-flare-up regimen (regardless of whether they received the flare-up regimen) during Part C.

Untreated (Never Received PVO Treatment) Group:

Untreated is defined as subjects who were not on the non-flare-up regimen and did not receive flare-up based treatment in Part C.

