4.3 Treated Population

The Treated Population will include all subjects who took at least one dose of palovarotene in Study PVO-1A-202 Part A. Analyses based on the Treated Population will generally be summarized in total. Note that data collected for flare-ups may use each flare-up as the unit of

analysis rather than each subject. The Treated Population will be the primary population for analysis of safety assessments performed at Flare-up Component visits.

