To assess an adequate number of flare-ups with the new dosing regimens, it is anticipated that each subject will participate in Part B of the study for approximately 18-24 months. Once a flare-up has resolved, the Adult Cohort subjects will resume non-flare-up based treatment of 5 mg once daily. Initiation of flare-up based treatment for a new flare-up can occur at any time after resolution of the prior flare-up.

Data regarding the original flare-up for those subjects from Study PVO-1A-201 will be collected at the Part B Screening visit (when the subject signs the informed consent) for the Adult Cohort according to the Schedule of Assessments in Table 1 of the Protocol; or at the Study Month 12 visit (starting from initial enrollment into Study PVO-1A-202) for the Pediatric Cohort according to the Schedule of Assessments in Table 3 of the Protocol.

Assessments for the Study Month 12 visit can be performed in conjunction with any of the site visits associated with flare-up based treatment (Flare-up Screening or Flare-up Day 84) as long

as those visits are within 5 months before or after the scheduled Study Month 12 visit. Subjects on Non-Flare-up dosing regimen will also be contacted by telephone at Study Months 6, 18, and 24 to assess concomitant medications and adverse events (AEs). The visit window is +/- 2 weeks where Day 1 is the date of informed consent for Part A.

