2.4 Study Treatment

Subjects in the Adult Cohort were scheduled to be treated with 5 mg palovarotene daily for up to 24 months (non-flare-up based treatment); however, some adult subjects chose not to receive non-flare-up based treatment.

Flare-up based treatment will begin as soon as possible after a subject reports onset of a flare-up and the flare-up has been confirmed by the Investigator. In the event of an eligible flare-up, subjects in the Adult Cohort will receive open-label palovarotene treatment as follows:

- 20 mg for 28 days. The first dose will be taken upon flare-up confirmation by the Investigator.
- 10 mg for 56 days, for a total flare-up treatment duration of 84 days; treatment may be extended if the flare-up is ongoing and continue until the flare-up resolves. Dosing will be extended in 4-week intervals and be based on clinical signs and symptoms as assessed by the Investigator.

Subjects not receiving non-flare-up based dosing will only be treated during eligible flare-ups and will receive weight-adjusted doses of 20 and 10 mg palovarotene as follows:

Weight Range Category	20-mg Equivalent	15-mg Equivalent	10-mg Equivalent	7.5-mg Equivalent*	5-mg Equivalent*
20 to <40 kg	12.5 mg	10 mg	6 mg	4 mg	3 mg
40 to <60 kg	15 mg	12.5 mg	7.5 mg	5 mg	4 mg
≥60 kg	20 mg	15 mg	10 mg	7.5 mg	5 mg

* In the event of dose de-escalation.

If the subject experiences intolerable side effects during flare-up based dosing, the dose may be reduced to the next lower dose; if the subject is already receiving the lowest possible dose, then study drug will be discontinued. Treatment may be extended after the 84-day treatment period (flare-up based dosing) if the flare-up is ongoing and continue until the flare-up resolves. Dosing will be extended in 4-week intervals based on clinical signs and symptoms as assessed by the Investigator, with remote visits performed every 2 weeks while on treatment. In the event the subject requires dose de-escalation due to an intolerable side effect for a previous flare-up, then the dose the subject will receive for a subsequent flare-up will be determined by the Investigator and the Medical Monitor.

After the Flare-up Day 84/EOT visit has been conducted and the flare-up is considered resolved, subjects in the Adult Cohort will resume the non-flare-up based treatment.

Subjects not receiving non-flare-up based dosing who do not experience an eligible flare-up will not be treated.

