3.1.3 Baseline for Subjects Never Receive PVO Treatment in Part C

For subjects who never received any PVO Treatment in Part C, baseline is defined as the most recent non-missing measurement on Part C Study Day 1.

If baseline is missing in Part C, then baseline will be based on assessment prior to first non-flare-up treatment in Part B.

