5.10 Compliance

Compliance is defined as (duration of treatment/expected duration of treatment). Calculation of duration of treatment is described in Section 3.2.3 and 3.2.4.

The expected duration of treatment is calculated as following:

- For non-flare-up treatment, expected duration of treatment is calculated as (last non-flare-up dose date – first non-flare-up dose date) – (sum of (all Flare-up cycle dosing periods)) + 1.
- For flare-up treatment, expected duration of treatment is calculated as total of expected flare-up cycle dosing periods across all flare-up cycles. Each expected flare-up cycle dosing period is defined as (last flare-up cycle dose date – first flare-up cycle dose date + 1).

Compliance will be summarized for the Treated Population with descriptive statistics. Compliance in category (<80%, ≥80%) will also be summarized for counts and percentages of subjects.

6 Efficacy Data

Unless otherwise stated, efficacy data will be summarized using Enrolled Population presented by groups: PVO 20/10 mg Only, PVO 5 mg, PVO Total and Never Received PVO Treatment. The PVO 20/10 mg Only group only includes subjects who did not take PVO 5 mg.

Imaging Reads

Imaging data includes results from low-dose WBCT scans (excluding head) and radiographs.

WBCT HO status and total HO volume or new HO volume will be summarized by visit. Those analysis will be included in the interim CSR. All other analysis will be presented in the final CSR.

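### Part C's descriptive 'Never Received PVO Treatment' column excludes only Part C dosing, and its baseline rules can put Part B treatment time into an 'untreated' change

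*SAP*

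**What the plan says.** All places are in the Part C SAP unless stated.

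- **Group rule, Section 2.4.** The heading is 'Untreated (Never Received PVO Treatment)'. The rule is "Untreated is defined as subjects who were not on the non-flare-up regimen and did not receive flare-up based treatment in Part C".
- **Source of subjects, Section 2.4.** "All subjects will have participated in Part B and no new subjects will be enrolled in Part C and D".
- **Where the column appears.** Section 6 states that "efficacy data will be summarized using Enrolled Population presented by groups: PVO 20/10 mg Only, PVO 5 mg, PVO Total and Never Received PVO Treatment". Section 4.1 makes the column a default for Enrolled Population analyses. Section 7 uses it for vital signs, laboratory values, ECG, physical examination, linear growth and suicidality at the regular visits.
- **Main baseline, Section 3.1.3.** "For subjects who never received any PVO Treatment in Part C, baseline is defined as the most recent non-missing measurement", taken on Part C Study Day 1.
- **Fallback baseline, Section 3.1.3.** "If baseline is missing in Part C, then baseline will be based on assessment prior to first non-flare-up treatment in Part B".
- **HO baseline, Sections 6.1 and 6.2.1.** Volume change and new HO are measured from a scan made before non-flare-up dosing began, in Part B or in Part C.
- **Earlier exposure.** Part B SAP Section 2.4 scheduled the Adult Cohort for 5 mg daily for up to 24 months, although some adults chose not to take it, and eligible flare-ups were treated. Part A SAP Section 4.3 also defines a treated group: "The Treated Population will include all subjects who took at least one dose of palovarotene in Study PVO-1A-202 Part A".

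**The concern.** A table column with this title will be read as drug-naive. The rule behind it admits anyone without palovarotene in Part C, including subjects who took it for months in Part B and then stopped. The printed label in Sections 4.1, 6 and 7 does not carry the words that limit it to Part C.

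The baseline rules make this more than a naming matter. For a previously dosed member, a baseline taken before Part B dosing makes the reported change cover a period on drug, in a column presented as having none. This reaches CAJIS, FOP-PFQ, PROMIS, laboratory and vital-sign changes through the fallback in Section 3.1.3, and HO through Sections 6.1 and 6.2.1. A reader who sets this column beside the palovarotene columns would be comparing intervals of different length and different exposure without being told.

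**Working it through.** There is no plan figure to reproduce. The check is a reading of the rules side by side, followed by one illustration.

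**1. Does the rule require no earlier dosing?** In Section 2.4 the words limiting the rule to Part C could be read as attaching only to the flare-up clause. Section 3.1.3 settles this: its title and first sentence both speak of no treatment in Part C. Nothing in the Part C SAP removes subjects with earlier palovarotene from the group.

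**2. Can members have been dosed earlier?** Yes. All came through Part B, and Part B, Part A or both may have included treatment. Passing through Part B does not prove dosing, because some adults declined and other subjects were treated only for eligible flare-ups.

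**3. What does the Section 3.1.3 fallback do?**

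| Member of the column | Part C Day 1 value present | Part C Day 1 value missing |
|---|---|---|
| Had non-flare-up drug in Part B | Part C baseline | Baseline before Part B dosing, so the change includes Part B treatment time |
| Had only flare-up drug in Part B | Part C baseline | Undefined: no such Part B date exists |
| Never dosed | Part C baseline | Undefined: no such Part B date exists |

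The fallback therefore either contradicts the column label or cannot be computed.

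**4. What happens for HO?** Section 3.1 applies its definitions unless otherwise stated, and Sections 6.1 and 6.2.1 state otherwise. A member given non-flare-up drug in Part B is measured from before that dosing even when a Part C Day 1 scan exists, in conflict with the main rule of Section 3.1.3. For a member never given non-flare-up drug, Sections 6.1 and 6.2.1 give no usable baseline.

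**5. Illustration of size.** Input: the Part B SAP, Section 2.3, where "it is anticipated that each subject will participate in Part B of the study for approximately 18-24 months". Assumptions: one subject takes palovarotene throughout Part B, there is no gap between parts, no drug is taken in Part C, and the baseline is the one before Part B dosing. With B months in Part B and the visit m months into Part C, the share of the interval on drug is B / (B + m). At m = 12:

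- B = 18: 18 / (18 + 12) = 18/30 = 60%
- B = 24: 24 / (24 + 12) = 24/36 = 67%

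The share falls at later visits. At m = 36 it is 18/54 = 33% to 24/60 = 40%. With a Part C Day 1 baseline it is zero at every visit.

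**The case against.** The strongest reply is that this is a display column and nothing is tested against it. That stands. Section 6.1 sends inference to Section 3.4, where Part C is compared with the natural history study, and Section 10 confirms this for the final report. A reader might infer that those comparisons are contaminated. By this route they are not. Section 9 does speak of comparisons solely within Part C, but it records a change made for the 2020 version.

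A reader might also infer that the mixed column dilutes or even reverses a treatment contrast by some calculable amount. The documents do not support that. They specify no estimated difference against this column, and they give neither the share of members dosed before nor how far any effect persists.

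Nor is this the only off-drug display. Section 7.1 has a Non-Treatment Period for adverse events, Section 5.8 gives flare-up rates during the interruption, and Section 7.9 has an off-treatment period for bone safety.

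On growth and bone safety the reply holds in part. Section 7.5 sets its own Part C screening baseline for linear growth, and Section 7.9 uses the first assessed timepoint in any study, so the Section 3.1.3 fallback does not reach them. The label can still reach them. Section 7 names the column for linear growth. Sections 7.9.1, 7.9.3 and 7.9.4 summarize bone age, knee alignment and growth-plate closure, limb length and hip findings in the Enrolled Population, which Section 4.1 presents by this column unless stated otherwise.

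Finally, the main rule in Section 3.1.3 is sound, and its fallback applies only when the Day 1 value is missing. That limits the fallback problem but not the HO problem, which does not depend on a missing value.

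**Conclusion.** The concern holds as a defect of definition and derivation in descriptive tables. Three things are wrong as written:

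- The label promises no palovarotene ever, while the rule requires none in Part C only.
- The Section 3.1.3 fallback fits only previously dosed subjects and is undefined for those never given non-flare-up drug.
- The HO baseline in Sections 6.1 and 6.2.1 conflicts with Section 3.1.3 for this group, and brings Part B treatment time into the change of previously dosed members.

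The extent is unknown, because the SAP does not say how many members were dosed earlier or lack a Part C Day 1 value. The 60% to 67% describes one subject under the stated assumptions; it does not estimate the effect on the column. Confidence is high on the mismatch in the text, and no claim is made about the direction or amount of bias. The correction should be made because it changes reported values and how a reader understands them.

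**What to change.** 1. In Sections 2.4, 3.1.3, 4.1, 6 and 7, rename the column 'Not treated in Part C'.
2. Split or flag it by any earlier palovarotene dose (PVO-1A-201, Part A or Part B), with time since last dose. Reserve 'Never Received' for subjects with none.
3. In Section 3.1.3, replace the fallback with the last non-missing value on or before Part C Study Day 1.
4. In Sections 6.1 and 6.2.1, use that same Part C baseline for this group's HO summaries. Changing Section 3.1.3 alone would leave HO measured from before Part B dosing.

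The cost is SAP wording, one exposure flag with time since last dose derived from dosing records, and a re-derived baseline for one column. The downside is a smaller never-treated column, possibly empty, and some subjects without a usable baseline. Both are better shown in the table than hidden by the label.
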